6. DOSING DELAYS/DOSE MODIFICATIONS

Dose delays and modifications will be made as indicated in the following table(s). The descriptions and grading scales found in the revised NCI Common Terminology Criteria for Adverse Events (CTCAE) version 5.0 will be utilized for dose delays and dose modifications. A copy of the CTCAE version 5.0 can be downloaded from the CTEP website http://ctep.cancer.gov/protocolDevelopment/electronic_applications/ctc.htm.

Neurologic toxicities per CTCAE v5.0 probably or definitely related to protocol therapy (not applicable to toxicities/symptoms secondary to intracranial tumor burden)	
grade 1 or 2	Continue radiation / AGuIX administrations
grade 3	Hold radiation / AGuIX administrations until \leq grade 2, then continue both radiation and AGuIX administrations
grade 4	Hold radiation 1 week and until \leq grade 2, then continue (no further AGuIX will be administered)

7. ADVERSE EVENTS: LIST AND REPORTING REQUIREMENTS

Adverse event (AE) monitoring and reporting is a routine part of every clinical trial. The following list of reported and/or potential AEs (Section 7.1) and the characteristics of an observed AE will determine whether the event requires expedited reporting **in addition** to routine reporting.

7.1. Adverse Event List(s) for AGuIX

As AGuIX nanoparticles were injected into few numbers of patients, and given the absence of toxicity reported during the regulatory preclinical studies, the list of potential toxicities has been established by analogy based on the product characteristics summary of gadolinium salts (Gadoteric acid (Dotarem®)), and from the Nano-Rad and NANORAD2 clinical trial safety results, and animal toxicological data of AGuIX (See AGuIX Investigator's Brochure).

Data from Gadoteric acid Summary of Product Characteristics:

System Organ Class (SOC) classification:

Immune system disorders

Uncommon: hypersensitivity

Very rare: anaphylactic reaction, anaphylactoid reaction

Psychiatric disorders

Rare: anxiety

Very rare: agitation

Nervous system disorders

Uncommon: headaches, dysgeusia, vertigo, somnolence, paresthesia

Rare: presyncope

Very rare: coma, seizure, syncope, tremor, parosmia

Eye disorders

Rare: eyelid edema

Very rare: conjunctivitis, ocular hyperemia, blurry vision, lacrimation disorder

Cardiac disorders

Rare: palpitations

Very rare: tachycardia, cardiac arrest, arrhythmia, bradycardia

Vascular disorders

Uncommon: hypotension, hypertension

Very rare: vasodilatation, pallor

Respiratory, thoracic and mediastinal disorders

Rare: sneezing

Very rare: cough, dyspnea, nasal congestion, respiratory arrest, bronchospasm, laryngospasm, pharyngeal edema, dry throat, pulmonary edema

Gastrointestinal disorders

Uncommon: nausea, abdominal pain

Rare: vomiting, diarrhea, salivary hypersecretion

Skin and subcutaneous tissue disorders

Uncommon: rash

Rare: urticaria, pruritus, hyperhidrosis

Very rare: erythema, angioedema, eczema

Undetermined frequency: nephrogenic systemic fibrosis

Musculoskeletal and systemic disorders

Very rare: muscular contractions, muscle weakness, back pain

General disorders and administration site conditions

Uncommon: feeling heat, feeling cold, injection site reactions, asthenia

Rare: chest pain, chills

Very rare: malaise, chest discomfort, fever, facial edema, injection site necrosis, superficial phlebitis

Data from animal toxicological data of AGuIX

Renal and urinary tract disorders

Incidence of renal failure not assessed because data are extrapolated from animal studies with AGuIX. A study in rats (reference Wil Research AB20679) showed the reversibility of the minimal tubular vacuolation phenomenon observed during drug elimination, after a recovery period of 10 weeks, following 2 IV injections at a high dose of 750 mg/kg (HED = 121 mg/kg).

Data from the Nano-Rad phase I clinical trial:

Summary of all serious adverse events (SAE):

Preferred term	Total	Possibly related*
Eye disorders		
Blindness	1	
Gastrointestinal disorders		
Oesophagitis	1	

General disorders and administration site conditions		
Cardiac death	1	
Disease progression	7	
General physical health deterioration	1	1
Infections and infestations		
Device related infection	1	
Sepsis	1	
Injury, poisoning and procedural complications		
Craniocerebral injury	1	
Delayed effects of radiation	1	1
Neoplasms benign, malignant and unspecified (incl cysts and polyps)		
Malignant neoplasm progression	4	
Malignant pleural effusion	2	
Neoplasm progression	1	
Nervous system disorders		
Epilepsy	1	
Intracranial pressure increased	1	
Leukoencephalopathy	1	1
Partial seizures	1	
Psychiatric disorders		
Confusional state	2	1
Respiratory, thoracic and mediastinal disorders		
Pulmonary embolism	2	

*These SAEs were related to radiotherapy and were considered as possibly related to study drug by the Sponsor, as AGuIX acts as a radiosensitizing agent.

Summary of non-serious adverse events:

Preferred Term	Total	Possibly/Probably linked to AGuIX	Low intensity	Moderate intensity
Blood and lymphatic system disorders				
Anaemia	1		1	
Thrombocytopenia	2		2	
Cardiac disorders				
Supraventricular extrasystoles	1			1
Ear and labyrinth disorders				
Hypoacusis	1		1	
Vertigo	1		1	
Endocrine disorders				
Hypothyroidism	1		1	
Gastrointestinal disorders				
Aphthous ulcer	1			1
Constipation	2			2
Diarrhea	1		1	
Nausea	6	1	4	2
Vomiting	2		2	
General disorders and administration site conditions				
Asthenia	4		1	3

Gait disturbance	1			1
Malaise	1			1
Pain	1		1	
Pyrexia	1			1
Infections and infestations				
Sinusitis	1			1
Metabolism and nutrition disorders				
Hypoglycaemia	1			1
Musculoskeletal and connective tissue disorders				
Musculoskeletal pain	1			1
Nervous system disorders				
Aphasia	1			1
Balance disorder	1			1
Cerebellar syndrome	1	1		1
Cognitive disorder	1		1	
Disturbance in attention	1		1	
Dysmetria	1		1	
Headache	6	2	3	3
Hemiplegia	1			1
Intracranial pressure increased	3	1	2	1
Memory impairment	1		1	
Paraesthesia	3		1	2
Parosmia	1			1
Psychomotor skills impaired	1		1	
Psychiatric disorders				
Confusional state	3	1	1	2
Reading disorder	1			1
Skin and subcutaneous tissue disorders				
Alopecia	1			1
Dermatitis	3	1	2	1
Dry skin	1			1
Livedo reticularis	1		1	

Data from the NANORAD2 phase II clinical trial:

Summary of all serious adverse events (SAE):

Preferred Term	WBRT	AGuIX + WBRT	Total
Infections and infestations			
Pyelonephritis acute	1		1
Sepsis	1		1
Subtotal	2		2
Neoplasms benign, malignant and unspecified (incl. cysts and polyps)			
Lung adenocarcinoma	1		1
Lung neoplasm malignant	1		1
Lymphangiosis carcinomatosa	1		1
Malignant neoplasm progression	1	1	2
Metastases to meninges	1	1	2
Neoplasm progression	1		
Subtotal	6	2	8
Nervous system disorders			

Preferred Term	WBRT	AGuIX + WBRT	Total
Aphasia	1		1
Cerebral oedema	1		1
Headache		1*	1
Hemiplegia	1		1
Intracranial pressure increased	1		1
Motor dysfunction	1	1	2
Neurological decompensation	1		1
Partial seizures		1	1
Pyramidal tract syndrome	1		1
Seizure	1		1
Subtotal	8	3	11
Respiratory, thoracic and mediastinal disorders			
Bronchial secretion retention		1	1
Dyspnoea		1	1
Pleural effusion		1	1
Pneumonia aspiration	1		1
Pulmonary embolism		1	1
Respiratory arrest		1	1
Respiratory distress	1	1	2
Subtotal	2	6	8
Gastrointestinal disorders			
Nausea	1		1
Rectal haemorrhage	1		1
Vomiting	1		1
Subtotal	3		3
Musculoskeletal and connective tissue disorders			
Spinal pain	1		1
Subtotal	1		1
General disorders and administration site conditions			
Asthenia	2		2
Death	1		1
Disease progression	2	3	5
General physical health deterioration	11	4	15
Subtotal	16	7	23
Psychiatric disorders			
Confusional state	1	1	2
Subtotal	1	1	2
Surgical and medical procedures			
Lesion excision		1	1
Subtotal		1	1
Injury, poisoning and procedural complications			
Fall		1	1
Subtotal		1	1
Investigations			
SARS-CoV-2 test positive	2		2
Subtotal	2		2
TOTAL	41	21	62

* This SAE was possibly related to radiotherapy and was considered as possibly related to study drug by the Sponsor, as AGuIX acts as a radiosensitizing agent.

7.1.1. Adverse Event List(s) for brain-directed stereotactic radiation (standard of care):

Immediate Reactions	Long-Term Reactions
Common:	Common:

 • Tiredness • Mild skin reddening & irritation • Temporary regional hair loss 	
 • Permanent hair loss
Uncommon	Uncommon:

 • Worsening of symptoms • Transient nausea or headache • Skin irritation from tight mask 	
 • Changes to bone, cartilage, or brain tissue. • Swelling of brain tissue
Rare:	Rare:

 • Tumor hemorrhage • Brain swelling causing neurologic symptoms • Stroke • Loss of speech • Weakness on one side • Numbness or tingling on one side 	
 • Loss of vision • Deafness • Paralysis • Stroke or brain hemorrhage • Radiation injury (necrosis) • Need for neurosurgery to remove damaged tissue or recurrence
Extremely Rare:	Extremely Rare:

 • Seizures • Death 	
 • Seizures • Total debilitation • Cancers caused by radiation

7.2. Adverse Event Characteristics

- **CTCAE term (AE description) and grade:** The descriptions and grading scales found in the revised NCI Common Terminology Criteria for Adverse Events (CTCAE) version 5.0 will be utilized for AE reporting. All appropriate treatment areas should have access to a copy of the CTCAE version 5.0. A copy of the CTCAE version 5.0 can be downloaded from the CTEP web site http://ctep.cancer.gov/protocolDevelopment/electronic_applications/ctc.htm.
- **Attribution** of the AE:
 - Definite – The AE *is clearly related* to the study treatment.
 - Probable – The AE *is likely related* to the study treatment.
 - Possible – The AE *may be related* to the study treatment.
 - Unlikely – The AE *is doubtfully related* to the study treatment.
 - Unrelated – The AE *is clearly NOT related* to the study treatment.

7.3. Expedited Adverse Event Reporting

- 7.3.1. In the event of an unanticipated problem or life-threatening complications treating investigators must immediately notify the study PI.
- 7.3.2. Investigators **must** report to the study PI any adverse event (AE) that occurs after the initial dose of study treatment, during treatment, or within 30 days of the last dose of treatment on the local institutional SAE form.
- 7.3.3. DF/HCC Adverse Event Reporting Guidelines

Investigative sites within DF/HCC will report AEs directly to the DFCI Office for Human Research Studies (OHRS) per the DFCI IRB reporting policy.

Attribution	DF/HCC Reportable Adverse Events (AEs)				
	Gr. 2 & 3 AE Expected	Gr. 2 & 3 AE Unexpected	Gr. 4 AE Expected	Gr. 4 AE Unexpected	Gr. 5 AE Expected or Unexpected
Unrelated Unlikely	Not required	Not required	5 calendar days [#]	5 calendar days	24 hours [*]
Possible Probable Definite	Not required	5 calendar days	5 calendar days [#]	5 calendar days	24 hours [*]
[#] If listed in protocol as expected and not requiring expedited reporting, event does not need to be reported.					
[*] For participants enrolled and actively participating in the study or for AEs occurring within 30 days of the last intervention, the AE should be reported within 1 business day of learning of the event.					

The study PI will submit AE reports from outside institutions to the DFCI OHRS according to DFCI IRB policies and procedures in reporting adverse events.

7.4 Reporting to Hospital Risk Management

Participating investigators will report to their local Risk Management office any participant safety reports, sentinel events or unanticipated problems that require reporting per institutional policy.

7.5 Reporting to the Food and Drug Administration (FDA)

The study PI, as study sponsor, will be responsible for all communications with the FDA. The study PI will report to the FDA, regardless of the site of occurrence, any serious adverse event that meets the FDA’s criteria for expedited reporting following the reporting requirements and timelines set by the FDA.

7.6 Routine Adverse Event Reporting

All Adverse Events **must** be reported in routine study data submissions to the study PI on the toxicity case report forms. **AEs reported through expedited processes (e.g., reported to the IRB, FDA, etc.) must also be reported in routine study data submissions.**

8. PHARMACEUTICAL INFORMATION

A list of the adverse events and potential risks associated with the investigational or other agents administered in this study can be found in Section 7.1.

8.1 IND Agent - AGuIX

8.1.1 Description

The chemical name of AGuIX is Gadolinium-chelated polysiloxane based nanoparticle and its formula is: $(\text{GdSi}_{3-8}\text{C}_{24-34}\text{N}_{5-8}\text{O}_{15-30}\text{H}_{40-60}, n\text{H}_2\text{O})_x$

AGuIX is a nanomedicine under investigation composed of gadolinium macrocyclic chelates covalently linked on a polysiloxane matrix (functionalized silica) created to improve radiotherapy efficacy through its imaging properties and radiosensitization effects.

8.1.2 Form

AGuIX presenting as a sterile lyophilized powder. Its primary packaging is carried out by the French subsidiary of Carbogen AMCIS in a 15 mL sterile glass vial with a bromobutyl rubber stopper containing 1g AGuIX as active ingredient and of CaCl_2 and NaCl as inactive ingredients.

8.1.3 Storage and Stability

The investigational product must be stored at $[+2^\circ\text{C}; +8^\circ\text{C}]$ in a clean and dry area until reconstitution. AGuIX reconstituted solution will be administered minimum 1 hour and maximum 24 hours after reconstitution. The solution can be stored up to half-day at room temperature and up to 24 hours at $[+2^\circ\text{C}; +8^\circ\text{C}]$ after reconstitution.

8.1.4 Handling

Qualified personnel, familiar with procedures that minimize undue exposure to themselves and the environment, should undertake the preparation, handling, and safe disposal of the agent in a self-contained and protective environment.

8.1.5 Availability

The expiry date will be checked by the pharmacist of the Dana-Farber/Brigham and Women's Hospital. The vials should be stored at $[+2^\circ\text{C}; +8^\circ\text{C}]$ in a clean and dry area, protected from the light until the reconstitution.

AGuIX is provided by investigational supply.

8.1.6 Preparation

The amount of sterile lyophilized AGuIX required will be determined according to the included

patient's data and the desired treatment dose. The corresponding number of vials will be prescribed by the investigator using the prescription provided.

Each 15 mL sterile glass vial containing 1 g of sterile lyophilized powder of AGuIX will be reconstituted with 10.00 mL of sterile water for injection to obtain a solution with a final concentration of 100 mg/mL. The pH of the solution is then at 7.3 ± 0.3 .

After reconstitution with water for injection, the reconstituted solutions will be taken into a syringe, before being injected using a syringe pump or Baxter pump.

8.1.7 Administration

The reconstituted solution of AGuIX should be administered as a continuous intravenous infusion using a rate-regulating device per institutional guidelines with associated pre-medications. It should not be administered as an IV push. It should be administered at a dose rate of 2 mL/min.

8.1.8 Accountability

The investigator, or a responsible party designated by the investigator, should maintain a careful record of the inventory and disposition of the agent using the NCI Drug Accountability Record Form (DARF) or another comparable drug accountability form. (See the NCI Investigator's Handbook for Procedures for Drug Accountability and Storage.)

8.1.9 Destruction and Return

Empty vials and/or reconstituted but not fully used AGuIX vials will be returned to the hospital pharmacy for accounting and destruction. Out of date and non-used vials will be maintained in quarantine until monitoring by the sponsor and will be returned to NH TherAguix.

8.1.10 Placebo

The placebo will consist of sterile normal saline. The volume of saline will mimic the volume of the AGuIX infusion in patients assigned to the experimental arm. Infusion times will be equivalent in the two cohorts. The process of masking AGuIX and the placebo is described above in section 5.1.

9. BIOMARKER, CORRELATIVE, AND SPECIAL STUDIES

N/A

10. STUDY CALENDAR

The study calendars below (calendars vary based on the exact type of radiation utilized) present the schedule of treatment and follow up visits. If a participant fails to appear for a visit, the investigator will make every attempt to contact them and determine the reason for the missed visit. Performance status will be assessed via the Karnofsky score. Quality of life will be assessed via the MDASI-BT: M. D. Anderson Symptom Inventory – Brain Tumor survey. General health status will be assessed via the EQ-5D. Quality of life, health status, and performance status will be assessed indefinitely (quality of life and performance status are assessed per usual care, as the MDASI-BT is the instrument used for the BWH initiative to obtain patient-reported outcome measures). Toxicity review will consist of a history at each visit to monitor for relevant toxicity. Neurocognitive assessments (Hopkins Verbal Learning Test - Revised (HVLT-R), Trail Making Test Part A and B (TMT), Controlled Word Association Test (COWAT), Mini Mental Status Examination (MMSE)) will be conducted at baseline and at 3 and 12 months post treatment; this cognitive battery takes 30 minutes to complete. MRIs of the brain will be obtained at 1.5, 3, 5, 7, and 9 months after radiation, and then every three months thereafter. Surveillance MRIs utilized in this study will be performed according to consensus recommendations for standardized brain tumor imaging protocol for clinical trials in brain metastases (BTIP-BM).⁴¹ Representative sequences will generally include but are not limited to 3D T1-weighted sequences with and without contrast in addition to axial T2-weighted sequences, T2 FLAIR, diffuse weighted imaging with ADC, susceptibility-weighted imaging, and dynamic susceptibility contrast (DSC) perfusion (with variations thereof deemed acceptable – e.g. use of fat saturation). If the above sequences cannot be obtained 3D T1-weighted sequences with and without contrast will be prioritized above others. For patients who clinically require more or less frequent MRIs of the brain (e.g. new symptoms warranting evaluation) the MRI and follow up schedule can be adapted if approved by the study PI. Post-radiation the use of whole brain radiation will be minimized, in lieu of stereotactic approaches, unless mandated by development of leptomeningeal disease develop or overwhelming distant intracranial recurrence without systemic agent viability. A participant will be deemed lost to follow-up only after at least 3 attempts to contact him/her have been made over a 3-week period. Participants will be followed until censoring (e.g. patient withdrawal, study completion) or death.

The length of follow up for the neurocognitive secondary endpoint will also be 12 months. The length of follow up for all other endpoints will be until censoring or death. Of note, the usual clinical care for patients with brain metastases involves a radiation oncology visit, history, and an MRI brain every 1.5-3 months until death or other loss to follow up. All secondary endpoints (with the exception of neurocognition and health status) are assessed as part of usual clinical care. Patients can elect to follow-up with a local provider following the completion of radiation if deemed appropriate by the study PI, in which case brain imaging must be retrieved and digitally stored. Providers will call patients whom elect to follow-up with a local provider to discuss imaging results and complete study documentation; in such cases quality of life testing and neurocognition do not need to be pursued.

Study calendars are presented here:

Patients managed with SRS

	Baseline ^a	Radiation Planning	2-5 Days Before Radiation Initiation	Radiation Day 1 ^b	Follow Up ^c	eDC Timepoints
Informed consent	X					
Medical history	X				X	Baseline
Karnofsky performance status	X				X	Baseline, Follow-up
CT simulation		X				Pre-Radiation
MRI brain			X ^d		X	Pre-Radiation, Follow-up
SRS				X		Radiation
AGuIX or placebo administration			X	X		Pre-Radiation, Radiation
Quality of life assessment	X				X	Baseline, Follow-up
Health status assessment	X				X	Baseline, Follow-up
Neurocognitive Assessment	X				X ^e	Baseline, Follow-up
Volumetric imaging	X				X	Baseline, Follow-up
AE assessment ^f	X		X ^g	X ^g	X	Baseline, Pre-Radiation, Radiation, Follow-up

Abbreviations: AE=Adverse Event; AGuIX=Activation and Guidance of Irradiation by X-ray; CT=Computed Tomography; MRI=Magnetic Resonance Imaging; SRS=Stereotactic Radiosurgery; SRT=Stereotactic Radiotherapy

a. Within 21 days

b. Within 14 days of radiation planning MRI

c. Follow up visits occur post radiation at approximately 1.5/3/5/7/9 months, and every 3 months thereafter (+/- 4 weeks except 1.5 month visit which is +/- 1 week)

d. To be performed before and after administration of AGuIX vs placebo

e. Neurocognitive assessments occur in the follow up period at 3 months and 12 months

f. For the purpose of this protocol, acute adverse events collected and documented on CRFs are only acute non-hematologic grade 3 or higher toxicities that did not predate radiation and are possibly, probably or definitely related to radiation/AGuIX

g. Adverse effects on days that AGuIX is administered will be assessed prior to administration of AGuIX

Patients managed with SRT (including those managed with SRS and SRT over 5 days)

	Baseline ^a	Radiation Planning	2-5 Days Before Radiation Initiation	Radiation Day 1 ^b	Radiation Day 2	Radiation Day 3	Radiation Day 4	Radiation Day 5	Follow Up ^c	eDC Timpoints
Informed consent	X									
Medical history	X									Baseline
Karnofsky performance status	X								X	Baseline, Follow-up
MRI brain			X ^d						X	Pre-Radiation, Follow-up
CT simulation		X								Baseline, Follow-up
SRS				X ^e						Radiation
SRT				X	X	X	X	X		Radiation
AGuIX or placebo administration			X	X		X				Pre-Radiation, Radiation
Quality of life assessment	X								X	Baseline, Follow-up
Health status assessment	X								X	Baseline, Follow-up
Neurocognitive Assessment	X								X ^f	Baseline, Follow-up
Volumetric imaging	X								X	Baseline, Follow-up
AE assessment ^g	X		X ^h	X ^h					X	Baseline, Pre-Radiation, Radiation, Follow-up

Abbreviations: AE=Adverse Event; AGuIX=Activation and Guidance of Irradiation by X-ray; CT=Computed Tomography; MRI=Magnetic Resonance Imaging; SRS=Stereotactic Radiosurgery; SRT=Stereotactic Radiotherapy

a. Within 21 days

b. Within 14 days of radiation planning MRI

c. Follow up visits occur post radiation at approximately 1.5/3/5/7/9 months, and every 3 months thereafter (+/- 4 weeks except 1.5 month visit which is +/- 1 week) d. To be performed before and after administration of AGuIX vs placebo

e. If indicated

f. Neurocognitive assessments occur in the follow up period at 3 months and 12 months

g. For the purpose of this protocol, acute adverse events collected and documented on CRFs are only acute non-hematologic grade 3 or higher toxicities that did not predate radiation and are possibly, probably or definitely related to radiation/AGuIX

h. Adverse effects on days that AGuIX is administered will be assessed prior to administration of AGuIX

Patients managed with SRS and SRT over 6 days:

	Baseline ^a	Radiation Planning	2-5 Days Before Radiation Initiation	Radiation Day 1 ^b	Radiation Day 2	Radiation Day 3	Radiation Day 4-6	Follow Up	eDC Timepoints
Informed consent	X								
Medical history	X								Baseline
Karnofsky performance status	X							X	Baseline, Follow-up
MRI brain			X ^d					X	Pre-Radiation, Follow-up
CT simulation		X							Baseline
SRS				X					Radiation
SRT					X	X	X		Radiation
AGuIX or placebo administration			X	X		X			Pre-Radiation, Radiation
Quality of life assessment	X							X	Baseline, Follow-up
Health status assessment	X							X	Baseline, Follow-up
Neurocognitive Assessment	X							X ^e	Baseline, Follow-up
Volumetric imaging	X							X	Baseline, Follow-up
AE assessment ^f	X		X ^g	X ^g				X	Baseline, Pre-Radiation, Radiation, Follow-up

Abbreviations: AE=Adverse Event; AGuIX=Activation and Guidance of Irradiation by X-ray; CT=Computed Tomography; MRI=Magnetic Resonance Imaging; SRS=Stereotactic Radiosurgery; SRT=Stereotactic Radiotherapy

a. Within 21 days

b. Within 14 days of radiation planning MRI

c. Follow up visits occur post radiation at approximately 1.5/3/5/7/9 months, and every 3 months thereafter (+/- 4 weeks except 1.5 month visit which is +/- 1 week) d. To be performed following before and after administration of AGuIX vs placebo

d. To be performed following before and after administration of AGuIX vs placebo

e. Neurocognitive assessments occur in the follow up period at 3 months and 12 months

f. For the purpose of this protocol, acute adverse events collected and documented on CRFs are only acute non-hematologic grade 3 or higher toxicities that did not predate radiation and are possibly, probably or definitely related to radiation/AGuIX

g. Adverse effects on days that AGuIX is administered will be assessed prior to administration of AGuIX

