AGuIX nanoparticles were combined with brain-directed radiation in the Nano-Rad clinical trial, in which patients received whole brain radiation in the presence of escalating doses of AGuIX. Evidence of increasing radiosensitization was seen at escalating doses of 15, 30, 50, 75, and 100 mg/kg.⁴⁰ No hemodynamic, cardiovascular, renal, hepatic, or other significant acute toxicities were noted. Of the 15 patients evaluated, no “in field” short or long-term grade IV toxicities were noted. One patient developed acute, in field, grade 3 toxicity (intracranial pressure increased); there were two in field late grade 3 toxicities (“confusional state” and “delayed effects of radiation”). In addition, 1 patient had “general physical health deterioration” that was listed as a possibly related SAE. Most SAEs on this study were felt to be related either to brain metastases, extracranial progression or other systemic treatment. Ten patients died during the follow up period of the study. Of these, nine deaths were considered not related to the experimental treatment while one death was felt to be related to disease progression with superimposed radiation related leukoencephalopathy. As a result of safety and early efficacy results, AGuIX based nanoparticles are being evaluated in multiple prospective phase II studies with 100mg/m² felt to be the optimal dose for brain-directed investigations (NCT03818386, NCT04094077) and are also being evaluated by other trials at BWH/DFCI (DFCI 19-826).

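### The calendars' AE footnotes limit CRF entry to undefined acute grade 3+ toxicities and give no rule for late ones, in conflict with Section 7.6 and at odds with Section 7.3.2

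*Protocol*

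**What the plan says.** Section 10 of the protocol has three calendars: SRS, SRT, and SRS plus SRT over 6 days. Each has an AE assessment row marked at Follow Up, with follow-up as an electronic data capture timepoint. Follow-up visits fall at about 1.5, 3, 5, 7 and 9 months and then every 3 months. The footnote on that row (f in the SRS and 6-day calendars, g in the SRT calendar) says that "acute adverse events collected and documented on CRFs are only acute non-hematologic grade 3 or higher toxicities". It adds that they must not predate radiation and must be at least possibly related to radiation or AGuIX.

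The text above the calendars says: "Toxicity review will consist of a history at each visit to monitor for relevant toxicity".

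Two other sections set a scope for AE reporting:

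- Section 7.6 requires that all adverse events "be reported in routine study data submissions to the study PI on the toxicity case report forms", with no limit on grade, timing or attribution.
- Section 7.3.2 requires investigators to report any AE to the study PI from the first dose until "within 30 days of the last dose of treatment", on the institutional SAE form.

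On earlier experience with AGuIX and whole brain radiation, Section 2.3 reports one acute in-field grade 3 toxicity and then says "there were two in field late grade 3 toxicities". These were a confusional state and delayed effects of radiation. It also says that "one death was felt to be related to disease progression with superimposed radiation related leukoencephalopathy".

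**The concern.** AGuIX is given to strengthen the effect of radiation in the brain, so late in-field injury is a plausible harm. The documents support this: two of the three in-field grade 3 toxicities in phase I were late. Section 7.1.1 lists loss of vision, deafness, paralysis and stroke among the long-term reactions to stereotactic radiation.

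The AE row is the only calendar entry that tells site staff which AEs go on the CRF, and its footnote speaks only of acute events. Read as a limit, it leaves out late events. Read as a threshold for acute events alone, it leaves the calendars with no rule for late ones. On either reading, what is recorded at month 7 depends on which section the site follows.

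At stake is the completeness of the randomised safety comparison for late related grade 3+ toxicities that are not endpoints. Section 13.1 lets this trial's result suggest a phase III trial. Late events that were never entered are hard to reconstruct afterwards.

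**Working it through.** No stated figure underlies this point, so the check sets the passages side by side.

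**Step 1. Scope of each rule**

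| Source | Grade | Attribution | Timing | Goes to |
|---|---|---|---|---|
| Section 10 footnotes | 3+, non-hematologic | at least possible | acute, not defined | CRF |
| Section 7.6 | all | all | no limit | toxicity CRF |
| Section 7.3.2 | any | any | to 30 days after last dose | study PI, SAE form |
| Section 7.3.3 table | 2 to 5, varying with expectedness and attribution | varies | no cut-off stated for grades 2 to 4 | institutional review office |

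The only time limit attached to *acute* anywhere is 1.5 months after the end of treatment, in the whole-cohort stopping rule of Section 13.4. That rule looks at the first six AGuIX patients only.

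**Step 2. One case under each rule.** Take a related grade 3 confusional state with onset at month 7.

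- Section 10 footnotes: excluded, or not addressed, depending on the reading.
- Section 7.3.2: the window has closed.
- Section 7.3.3: no report if expected; a report within 5 calendar days if unexpected. Confusional state and leukoencephalopathy stand in the Section 7.1 tables, and loss of vision, deafness, paralysis and stroke in Section 7.1.1. A site could therefore class them as expected.
- Section 7.6: must be entered.

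The footnotes and Section 7.6 give different answers for the same event, and the protocol does not say which prevails.

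**Step 3. What the endpoints already capture.** Sections 1.3 and 13.6 compare radiation necrosis, seizures and salvage craniotomy between arms as time-to-event outcomes. Performance status, activities of daily living, steroid use, quality of life and neurocognition are compared longitudinally. Neurocognition is followed for 12 months; for the rest, "The length of follow up for all other endpoints will be until censoring or death". Confusional state, leukoencephalopathy, loss of vision, deafness, paralysis and stroke are not endpoints. Cognitive tests are scheduled only at 3 and 12 months. Section 10 waives both these and quality of life testing for patients followed by a local provider.

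**Step 4. The phase I figure, for orientation.** Inputs: two late events (Section 2.3) and the denominator in "Of the 15 patients evaluated"; about 67 patients per arm (Section 13.2).

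- If the two events were in different patients: 2/15 = 13.3%, exact (Clopper-Pearson) 95% interval 1.7% to 40.5%. Times 67: 8.9 patients (1.1 to 27.1).
- If both were in one patient: 1/15 = 6.7%, interval 0.2% to 31.9%. Times 67: 4.5 patients.

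These figures describe how often such toxicity might occur. They do not measure how many events would be missed.

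**The case against.** The grammatical subject of the footnote is acute adverse events, so it may only set a threshold for those and bar nothing else. Section 7.6 requires all AEs on the CRFs. The Section 7.3.3 table asks for related unexpected grade 2 and 3 events, for grade 4 events (with an exception for some listed expected ones) and for all deaths. Section 7.6 then requires events reported that way to be entered in routine data as well. Section 13.7.1 makes patients evaluable for toxicity from first treatment with no end date. On this view the residual gap is mainly expected late grade 3 events, and only where staff let the footnote override Section 7.6.

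Most of this stands, and it rules out some stronger readings. A reader might infer that late severe toxicities will go unrecorded. That does not follow while Section 7.6 is in force. A reader might also infer that late safety cannot be compared between arms. That is wrong: Section 2.1 names radiation necrosis as the primary long-term adverse effect of stereotactic radiation, and it is a between-arm endpoint. Nor can it be said that the DSMB would see no late events, since Section 12.2 lists all reported AEs and SAEs among what it may receive.

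What does not stand is that Section 7.6 settles the matter. It is a general sentence set against a specific instruction repeated in three calendars, and no order of precedence is stated. The DSMB can receive only what has been reported.

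**Conclusion.** The point holds as an internal contradiction that affects which safety data will exist. Three scopes for AE recording are in force, *acute* is undefined where it is used for collection, and the calendars give no rule for late events. If the calendars are followed, late related grade 3+ toxicities outside the named endpoints may not be recorded or compared between arms.

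The size of the loss cannot be computed from the protocol. It depends on which rule staff apply and on which events they class as expected. The phase I rate of 2 in 15 should not be read as a forecast that about 9 AGuIX patients would have a missed event. It assumes that the two events were in different patients and that uncontrolled whole-brain experience at several dose levels carries over to stereotactic treatment. Some such events would also be captured as necrosis. The conclusion does not rest on that figure.

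**What to change.** - In the AE footnote of all three calendars, replace *only acute* with *acute and late*, keeping the non-hematologic, grade 3+ and at-least-possibly-related limits. State that these events are recorded with onset date at every follow-up visit until death or censoring.
- Define *acute* by a time limit, and say whether the 1.5 months of Section 13.4 is meant.
- Reconcile the footnotes with Sections 7.3.2 and 7.6 so that one stated scope governs CRF collection. Section 7.6 currently covers all AEs. If the sponsor chooses to narrow it, the text should say so openly, so that the wider scope is not lost as a side effect of alignment.
- Tabulate late events by arm for the DSMB and the final report.

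The cost is wording in three footnotes and two sections, a CRF field, and a few more entries per patient. The visits and AE assessments already take place. The change concerns data collection only.
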